^m Of note, for the eIV cohorts please reference protocol details for dosing. Day 1 eIV will be over day 1 and 2 (eg, ■ μg dose will be infused over days 1 and 2 [48 hours]), day 3 eIV infusion will be over day 3 only (eg, ■ μg over 24 hours), day 5 and day 8 will be short term IV infusions (~ 90 minutes each).

^e See protocol Section 6.2.1.1 for details on hospitalization requirements and in case of dose step. Subjects should be monitored intensively for at least 4 hours after the start of dose for clinical signs (eg, fever, hypotension, tachycardia, dyspnea, tremors) and laboratory changes (eg, transaminase increase) which may be related to cytokine release syndrome (CRS).

^f Collect anti-AML treatments only.

^g Vital signs/pulse oximetry will also be assessed prior when the subject leaves the clinic in order to detect possible signs and symptoms of infusion reactions.

^h Time points for vital sign and pulse oximetry measurements after the end of dose time point apply only if the subject is still at the clinic at the time.

ⁱ Premedication should be administered within 1 hour before the start of dose and prior to each step-up dose of AMG 427 dose to mitigate the risk for the prevention of CRS.

^j Blood must not be drawn from the port catheter during investigational product infusion and for 5 minutes after the end of infusion. If sample processing/shipment is not logistically feasible for a certain time point (eg, in case it coincides with the weekend) this sample time point is not mandatory.

^k For cycles 4 through cycle 12: ONLY predose PK samples are collected (predose: D1, D3, D5, D8, D12, D19). EOT and SFU also to be collected cycles 4 through 12.

^o If applicable, urine pregnancy test required 4 weeks after the last dose of AMG 427.

^q Of note, for the eIV cohorts please reference protocol details for dosing. Day 1 eIV will be over day 1 and 2 (eg, ■■■ μg dose will be infused over days 1 and 2 [48 hours]), day 3 eIV infusion will be over day 3 only (eg, ■■■ μg over 24 hours), day 5 and day 8 will be short term IV infusions (~90 minutes each).

Table 22. Schedule of Assessments: MRD+ Group Only - Whole Blood MRD Collection (Days 1, 3, 5, and 8)

MRD+ Whole Blood Collection (Day 1, 3, 5, 8)				
Cycle	Cycle 1		Cycle ≥ 2	EOT
Week	1		1	
Cycle Day	1	14	14	
Hours	Pre-dose			
Whole blood MRD (MRD cohort only)				
Whole blood MRD (MRD cohorts only) ^a	X ^a	X ^a	X ^a	X ^a

EOT = End of Treatment; MRD = minimal/measurable residual disease; MRD+ = minimal/measurable residual disease-positive

^a MRD+ groups will follow all Schedule C (Table 16 through Table 21) for all collections. Additionally, MRD+ cohorts will collect whole blood MRD at the following timepoints for all cycles.

Table 23. Schedule of Assessments: MRD+ Group Only – Whole Blood MRD Collection (Days 1, 3, 5, 8, 12, and 19)

MRD+ Whole Blood Collection (Day 1, 3, 5, 8, 12, and 19)				
Cycle	Cycle 1		Cycle ≥ 2	EOT
Week	1	4	4	
Cycle Day	1	28	28	
Hours	Pre-dose			
Whole blood MRD				
Whole blood MRD (MRD cohorts only) ^a	X ^a	X ^a	X ^a	X ^a

EOT = End of Treatment; MRD = minimal/measurable residual disease; MRD+ = minimal/measurable residual disease-positive

^a MRD+ cohorts will follow all Schedule C (Table 16 through Table 21) for all collections. Additionally, MRD+ cohorts will collect whole blood MRD at the following timepoints for all cycles.

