3.1.1 Dose Escalation

The study will have 3 alternative dosing schedules:

- **(CLOSED)** Schedule A
 - D1/D5 or D1/D5/D12/D19 (dexamethasone prophylaxis)
- **(CLOSED)** Schedule B: Etanercept Substudy (R/R AML)
 - D1/D5 or D1/D5/D12/D19 (etanercept 2 days prior to each cycle).

The etanercept substudy used etanercept 2 days prior to infusion of each cycle D1, and if applicable, 2 days prior to infusion on D12. [REDACTED]

- **Schedule C** (Table 16 through Table 21): FIH, eIV (R/R AML); MRD+ Group (MRD+ AML)
 - D1/D3/D5/D8 or D1/D3/D5/D8/D12/D19 (dexamethasone prophylaxis)

Note:

- The MRD+ group will use Schedule C for all cycle collections and Table 22 for additional whole blood MRD collection, or Table 23, as applicable.

The initial cohort will begin with Schedule A and will receive 2 doses (1 each on D1 and D5). After reviewing the emerging PK, safety and efficacy data, the DLRT may recommend the administration of additional doses on D3 and D8, to comprise a 2-week cycle with doses on D1/D3/D5/D8 (Schedule C).

[figure not shown]
Additionally, if the following conditions are met, the DLRT may recommend the administration of 2 additional doses (D12 and D19):

- the 2-4 dose regimen (D1/D5 and/or D1/D3/D5/D8) is deemed safe and tolerable
- it is determined from the observed AMG 427 exposures that AMG 427 is rapidly cleared and/or distributed (ie, its observed half-life is much shorter than its predicted half-life)
- efficacy (based on clinical data and pharmacodynamic markers eg, clearance of FLT3⁺ blasts in the blood and/or bone marrow) is observed but is not sustained and addition of D12 and D19 doses may improve the duration or depth of response

Once the DLRT recommends additional doses, all subsequent cohorts will be treated with a 4 or 6 dose regimen in each cycle. The additional doses (if applicable), may be at

the same dose as the preceding dose or may be at higher doses (dose step). A dose step is any dose that is higher for a given subject than the subject has previously received. Dose steps may occur at D3, D5, D8, D12, or D19 infusions.

Starting with an initial lower dose may improve tolerability of subsequently administered higher doses due to initial reduction of the bulk of blast cells, thereby improving efficacy. The DLRT will recommend an initial lower dose, which will not be higher than dose which triggered a DLT. For a schematic overview of the different dose step options see [Figure 2](#) below.

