3.1.1.1 FIH Group

The FIH group will evaluate AMG 427 administered as a short-term IV infusion in adult subjects with R/R AML. In escalation, approximately 90 subjects with R/R AML will be a part of FIH cohorts [REDACTED] (Table 4). Approximately 25 subjects with R/R AML will receive etanercept for CRS prophylaxis 2 days prior to their cycle and follow guidance below. **The option for group extension may be available, either at sponsor discretion or if recommended by the DLRT based on the review of the emerging safety data. The sponsor will notify sites, if applicable, when the extended slots for a group are open for enrollment after DLRT has confirmed the dose level is safe.**

3.1.1.2 eIV Infusion Group

The eIV group will evaluate AMG 427 administered as an eIV infusion in approximately 10 subjects with R/R AML. The study will be conducted in dose escalation, to explore and identify if alternative dosing of AMG 427 leads to an improved benefit/risk profile. The option for group extension may be available, either at sponsor discretion or if recommended by the DLRT based on the review of the emerging safety data. The sponsor will notify sites, if applicable, when the extended slots for a group are open for enrollment after DLRT has confirmed the dose level is safe. If improvement is seen in the benefit/risk profile for these subjects, eIV administration may be implemented in the ongoing FIH (short IV) dose escalation cohorts, as well as expansion cohorts.

Utilizing Schedule C, the eIV study design will consist of eIV and short IV infusions of AMG 427 administered on days 1 **and** 2, 3, 5, and 8.

- Days 1 and 2 will consist of the D1 dose administered as an eIV infusion over 48 hours (approximately 12-hour IV bag changes).
- Day 3 will consist of the D3 dose administered as an eIV infusion over 24 hours (approximately 12-hour IV bag changes).
- The remaining 2 doses (D5 and D8) will be regular short IV infusions (approximately 90 minutes) on day 5 and day 8.

The first eIV group will start at a DLRT-approved dose level from the FIH group as described in Section [6.2.1.1](#).

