Cytokine release is an anticipated consequence of T cell engagement induced by AMG 427. Cytokine release syndrome, including serious events **and a fatal event**, has been reported **in subjects** receiving AMG 427 in the clinical trial. Subjects may be at an increased risk for CRS during the first few days following the initial dose of AMG 427 and after a dose step. **More severe cases of CRS and/or ICANS have also been associated with higher tumor burden in multiple malignancies including leukemia, lymphoma, and multiple myeloma, which is likely to be associated with greater expansion of T cell populations and synchronous activation with BiTEs. Please refer to the Investigator’s Brochure for additional information.**

Infusion reactions may be clinically indistinguishable from manifestations of CRS. Throughout the infusion with AMG 427 and at least **12** hours after the start of infusion, monitor subjects intensively for clinical signs (eg, fever, hypotension, tachycardia, dyspnea, tremors) and laboratory changes (eg, increase **in transaminases, C-reactive protein [CRP], lactate dehydrogenase [LDH], ferritin, D-dimer, and erythrocyte sedimentation rate [ESR]**) which may be related to CRS. Cytokine release syndrome may be clinically associated with the development of fever, nausea, chills, hypotension, tachycardia, asthenia, headache, rash, scratchy throat, dyspnea, **and ICANS/neurotoxicity** as a consequence of systemic release of cellular cytokines such as TNF, **IL-1Ra**, IL-2, IL-3, IL-4, and IL-6 (**Morris et al, 2021; Winkler et al, 1999**). Potentially life-threatening complications of CRS include cardiac dysfunction, adult respiratory distress syndrome, renal and/or hepatic failure, and disseminated

intravascular coagulation (Lee et al, 2014) and **ICANS/neurotoxicity which may occur concurrently or immediately following CRS.**

Grading of CRS should be performed according to the guidelines provided in **Table 6** and management of CRS should be performed according to the guidelines provided in **Table 7** (based on the adopted grading system referenced in Lee et al, 2019).

Table 6. Cytokine Release Syndrome Grading (ASTCT; Lee et al, 2019)

CRS Parameter	Grade 1	Grade 2	Grade 3	Grade 4
Fever ^a	Temperature $\geq 38^{\circ}\text{C}$	Temperature $\geq 38^{\circ}\text{C}$	Temperature $\geq 38^{\circ}\text{C}$	Temperature $\geq 38^{\circ}\text{C}$
		With		

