AMG 427 dose ^g		X													X												X														
Premedication ⁱ	X											X												X																	
BIOMARKER ASSESSMENTS																																									
PK ASSESSMENTS																																									
AMG 427 PK ^k		X	X ^e			X					X	X	X ^e										X	X	X ^e				X	X			X	X			X	X	X		
DISEASE & BIOMARKER ASSESSMENTS																																									

ECG = electrocardiogram; ECOG = Eastern Cooperative Oncology Group; eGFR = estimated glomerular filtration rate; eIV = extended IV; IV = intravenous;

PK = pharmacokinetic; SCR = Screening

^a The Dose Level Review Team may recommend to change timing of D3, D5, D8 within a window of ± 1-3 days. In this case, timing of the following visits would be adjusted accordingly.

^b Collect assessments at the end of infusion (EOI). For the First-in-Human cohorts: End of infusion time is defined as the time at which the total infusion is complete (end of investigational product AMG 427 and flush infusion). Collect assessments after total infusion time is complete (ie, short IV ~ 90 minutes, eIV~ 24 hours).

^c See protocol Section 6.2.1.1 for details on hospitalization requirements and in case of dose step. Subjects should be monitored intensively for at least 4 hours after the start of dose for clinical signs (eg, fever, hypotension, tachycardia, dyspnea, tremors) and laboratory changes (eg, transaminase increase) which may be related to cytokine release syndrome (CRS).

^d Vital signs/pulse oximetry will also be assessed prior to subject's discharge from hospital in order to detect possible signs and symptoms of infusion reactions.

^e Schedule for triplicate ECGs during cycle 1 also applies in case of intra-subject dose escalation, regardless of actual study cycle.

^f Two (2) sets of triplicate ECGs collected at Screening.

^g Serum pregnancy test will be performed for all females unless surgically sterile or ≥ 2 years postmenopausal.

^h The estimated glomerular filtration rate (eGFR) will be calculated based on institutional standards

ⁱ Premedication should be administered within 1 hour before the start of AMG 427 dose and prior to each step-up dose of AMG 427 dose to mitigate the risk for the prevention of CRS.

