^e See protocol Section 6.2.1.1 for details on hospitalization requirements and in case of dose step. Subjects should be monitored intensively for at least 4 hours after the start of dose for clinical signs (eg, fever, hypotension, tachycardia, dyspnea, tremors) and laboratory changes (eg, transaminase increase) which may be related to cytokine release syndrome (CRS).

^f Collect anti-AML treatments only.

^g Vital signs/pulse oximetry will also be assessed prior when the subject leaves the clinic in order to detect possible signs and symptoms of infusion reactions.

^h Time points for vital sign and pulse oximetry measurements after the end of dose time point apply only if the subject is still at the clinic at the time.

ⁱ Premedication should be administered within 1 hour before the start of dose and prior to each step-up dose of AMG 427 dose to mitigate the risk for the prevention of CRS.

^j Blood must not be drawn from the port catheter during investigational product infusion and for 5 minutes after the end of infusion. If sample processing/shipment is not logistically feasible for a certain time point (eg, in case it coincides with the weekend) this sample time point is not mandatory.

^k For cycles 4 through 12, only predose PK samples are collected (Predose: D1, D3, D5, D8), EOT and SFU for cycles 4 through 12. Day 8 PK collection will not be collected C4 and beyond.

^o If applicable, urine pregnancy test required 4 weeks after the last dose of AMG 427.

^q Of note, for the eIV cohorts, please reference protocol details for dosing. Day 1 eIV will be over day 1 and 2 (eg, ■■■ μg dose will be infused over days 1 and 2 [48 hours]), day 3 eIV infusion will be over day 3 only (eg, ■■■ μg over 24 hours), day 5 and day 8 will be short term IV infusions (~90 minutes each).

^g Serum pregnancy test will be performed for all females unless surgically sterile or ≥ 2 years postmenopausal.

^h The estimated glomerular filtration rate (eGFR) will be calculated based on institutional standards

ⁱ Premedication should be administered within 1 hour before the start of dose and prior to each step-up dose of AMG 427 dose to mitigate the risk for the prevention of CRS.

^j Whole blood for peripheral blood mononuclear cells (PBMCs) collected prior to the dose on cycle 1 day 1 only if subject provides consent for collection of the pharmacogenetic (PG) sample.

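### The open Schedule C tables set a 4-hour minimum for intensive CRS monitoring where Section 6.6 sets 12 hours

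*Protocol*

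**What the plan says.** Section 6.6 (Cytokine Release Syndrome) instructs sites as follows: "Throughout the infusion with AMG 427 and at least 12 hours after the start of infusion, monitor subjects intensively for clinical signs", and also for related laboratory changes. It identifies an "increased risk for CRS during the first few days following the initial dose of AMG 427 and after a dose step".

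The Schedule C assessment tables in Section 7.1 carry a footnote on the same activity: "Subjects should be monitored intensively for at least 4 hours after the start of dose for clinical signs". It appears under Table 16 (footnote c), Table 18 (e), Table 20 (c) and Table 21 (e). The Table 21 block is identified by its position before Table 22 and by its pharmacokinetic footnote for later cycles: "ONLY predose PK samples are collected (predose: D1, D3, D5, D8, D12, D19". Each of these footnotes sends the reader to Section 6.2.1.1 for hospitalization; none mentions Section 6.6. The matching footnotes of Tables 17 and 19 are not legible in the public copy and were not checked.

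Tables 18, 20 and 21 also state that vital-sign and oximetry "measurements after the end of dose time point apply only if the subject is still at the clinic at the time".

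Section 6.2.1.1 sets the hospitalization rules:
- **Mandatory:** at least 8 or 11 days in cycle 1, and in cycle 2 at the same dose; 72 hours after days 12 and 19 of cycle 1; 72 hours after a dose step, an intra-subject escalation, or a restart following an adverse event.
- **At the physician's discretion:** days 12 and 19 from cycle 2, and every dose from cycle 3.
- **Expansion:** requirements may be reduced if the Dose Level Review Team (DLRT) so recommends.

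**The concern.** Two parts of the current protocol give different minimum durations for one safety procedure, with no rule of precedence. Section 7.2 tells sites to make every effort to follow the Schedules of Assessments, so the table is the text a site is likely to work from on a dosing day. A site could monitor to 4 hours, let the subject go home, and believe that it had complied.

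CRS is the main toxicity of this product. Section 2.2.4 reports it in 42 of 53 subjects (79.2%), as a serious event in 8 (15.1%), and as one fatal event. The Amendment 7 rationale says that the current protocol was written after that fatal case led to a partial clinical hold, and that better patient monitoring was one of its aims. The CRS monitoring period is therefore a poor place for two values.

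**Working it through.** No sample size, power or error rate is involved. The check compares the texts and then counts the doses affected.

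**Step 1. The difference between the two floors.** Both clocks start when the infusion or dose starts.

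| Dose type | Section 6.6 minimum | Footnote minimum | Difference |
|---|---|---|---|
| Short infusion, about 1.5 h | 12 h | 4 h | 12 − 4 = 8 h |
| Extended infusion (eIV), 24 h | 24 h (whole infusion) | 4 h | 24 − 4 = 20 h |
| Extended infusion (eIV), 48 h | 48 h (whole infusion) | 4 h | 48 − 4 = 44 h |

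For a short infusion, the footnote lets intensive monitoring end 4 − 1.5 = 2.5 hours after the infusion, against 12 − 1.5 = 10.5 hours under Section 6.6.

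The extended-infusion rows are differences in wording only. The still-at-clinic footnotes release time points after the end of dose, so checks during a 24- or 48-hour infusion stay in force.

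**Step 2. Where the difference can have an effect.** During mandatory hospitalization the subject is in hospital anyway, and in cycle 1 Table 16 schedules vital signs at 6, 8, 12, 16 and 20 hours. The difference matters where a short infusion is given, hospitalization is discretionary, and the later checks depend on the subject still being present. A subject released at 4 hours then misses the 6-, 8- and 12-hour checks.

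**Step 3. Counting those doses.** Let *n* be the number of cycles received (*n* ≥ 2), with the dose unchanged and no restart after an adverse event. In eIV cohorts only the short doses count. Section 3.1.1.2 says of days 5 and 8: "The remaining 2 doses (D5 and D8) will be regular short IV infusions (approximately 90 minutes". Days 12 and 19 are assumed to be short infusions as well.

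- Short-infusion cohort, 4 doses per cycle: 4(*n* − 2) of 4*n*
- Short-infusion cohort, 6 doses per cycle: 2 + 6(*n* − 2) of 6*n* (days 12 and 19 of cycle 2, then every dose)
- eIV cohort, 4 doses per cycle: 2(*n* − 2) of 4*n*
- eIV cohort, 6 doses per cycle: 2 + 4(*n* − 2) of 6*n*

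| Cycles | Short, 4-dose | Short, 6-dose | eIV, 4-dose | eIV, 6-dose |
|---|---|---|---|---|
| 2 | 0/8 | 2/12 | 0/8 | 2/12 |
| 3 | 4/12 | 8/18 | 2/12 | 6/18 |
| 12 (ceiling) | 40/48 | 62/72 | 20/48 | 42/72 |

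The 6-dose columns apply only if the DLRT adds days 12 and 19, which Section 3.1.1 makes conditional. The last row is the maximum the protocol permits, not an expectation.

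**Step 4. Expansion.** If the DLRT reduces hospitalization there, earlier doses could be exposed too. In cycle 1 the fixed checks of Table 16 would still stand, because none of its legible footnotes releases them.

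**The case against.** The strongest reply is that nothing strictly conflicts. Both figures are floors, 12 hours meets both, and the footnote does not say that monitoring may stop or that the subject may leave at 4 hours. The riskiest doses are given in hospital. Other safeguards exist: Tables 18, 20 and 21 require vital signs and oximetry when the subject leaves, and Table 7 requires checks at least every 2 hours, for 12 hours or until resolution, once even grade 1 CRS appears. The dose counts show where hospitalization is discretionary, not where monitoring would actually be cut short, and the documents do not say how many subjects reach cycle 3. Section 6.6 is also headed as recommendations, and a 12-hour stay at every later dose is a real burden.

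Much of this stands, and it limits the size of the point. It does not remove it. The check on leaving and the Table 7 rules catch CRS that has already begun; neither covers onset between 4 and 12 hours in a subject who has gone home. The sentence in Section 6.6 is a direct instruction despite its heading, and the footnotes are themselves worded as advice, so the heading does not make 4 hours the governing figure. The burden of a longer stay already follows from Section 6.6.

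**Conclusion.** The concern holds. The current protocol gives two minimums, 12 and 4 hours, for the same CRS monitoring in its only open schedule, and does not say which applies. This is an internal inconsistency that should be fixed; it does not undermine the design.

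Its size is 8 hours for a short infusion, mainly at doses with discretionary hospitalization. After three cycles at an unchanged dose, these are 4 of 12 or 8 of 18 doses in short-infusion cohorts and 2 of 12 or 6 of 18 in eIV cohorts. The counts assume no dose step, escalation or restart; the 6-dose figures also need a DLRT decision, and the eIV 6-dose figure assumes that days 12 and 19 are short infusions. They are doses at which early release is possible, not a forecast of under-monitoring. Without CRS onset times, no number of missed events can be given.

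**What to change.** 1. Reword the monitoring footnotes of Tables 16, 18, 20 and 21 to cover the whole infusion and not less than 12 hours from its start, with a cross-reference to Section 6.6.
2. Check the corresponding footnotes of Tables 17 and 19 and align them if needed.
3. State in the still-at-clinic footnotes (Table 18 h, Table 20 e, Table 21 h) that they do not shorten the Section 6.6 period.
4. Notify sites.

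The cost is a footnote edit and a site notice. Some later-cycle short infusions will mean a longer clinic stay, which Section 6.6 already requires. No new fixed vital-sign time points are needed.

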7.2 General Study Procedures

A signed and dated IRB/IEC approved ICF must be obtained prior to performing any study-specific procedures including discontinuing standard therapy for observing a study washout period.

During the study, every effort should be made to perform the study procedures as indicated on the Schedules of Assessments (Table 10 to Table 23). Every effort should be taken to collect all biomarker and PK samples as described in the schedule of assessments. However, if sample processing/shipment on a weekend/holiday is not logistically feasible for a site, this needs to be documented and will not be considered a deviation from the protocol.

Subjects will be seen in the clinic for study evaluations. When electrocardiograms (ECGs), vital signs, blood sample collections, biomarker sample collections, and aspirate/biopsy sample collections occur on the same visit, ECGs and vital signs should be performed before samples (blood, biopsy/aspirate) are collected. Blood samples must not be taken/drawn from the catheter port used for AMG 427 infusion. If a permanent central line with more than 1 lumen is used, blood draws can be done via the lumen that is not used for drug administration (see also Section 7.3.15). The time of blood sample collection must be recorded with the exact time of collection (do not use the time that the samples were frozen or any other time point).

The study specific manuals provide additional details regarding the requirements for these procedures.

Acceptable deviation windows are as follows:

- Infusion duration \pm 10 minute window.
- ECGs, biomarker blood draws (cycles 1 – 3), vital signs (including pulse oximetry):
 - \pm 15 minute window if collected within the first 24 hours (excluding the 24 hour sample) after the start of any dose
 - \pm 2 hour window if collected between 24 hours and 3 days after the start of any dose
 - Assessments after day 3 but within 7 days post infusion start should be performed on the indicated study day, but are not required at a certain hour of the day
 - Assessments after day 7 have a \pm 1 day window
- For R/R AML subjects, bone marrow assessments post treatment start: \pm 3 days

- For MRD+ subjects, bone marrow assessments do not need to be repeated if done within 3 months prior to start of treatment with AMG 427. If more than 3 months have passed, discuss with medical monitor prior to performing.
- PK blood draws in cycles 1 - 3:
 - within 2 hours prior to infusion start
 - \pm 15 minute window for samples taken after the end of each dose
 - Blood must not be drawn from the port catheter during infusion and for 5 minutes after the end of infusion. End of infusion (EOI) is defined as end of total infusion time (after investigational product and IV flush infusion).

For dosing visits a \pm 1 - 3 day time window applies.

Local laboratories should be used for the following assessments: hematology, hematological bone marrow assessments, clinical chemistry, coagulation, urinalysis, hepatitis serology, and serum pregnancy tests. The following collections will be shipped to a central laboratory for analysis: blood samples for determination of serum concentrations of AMG 427 and presence of [REDACTED].

Refer to the laboratory manual for detailed collection, processing, and shipping procedures.

Additional procedures deemed necessary as part of standard of care or as required by local laws and regulations may be performed at the Investigator's discretion.

